[D3] Total WBC count <2000 cells/ μ L	Monitor and Stats	Monitor’s list, or, If a patient still receives study treatment after 10 days of latest dose with confirmed total WBC count <2000 cells/ μ L (defined as a test and a retest within 10 days); If no retest, use the test results
[D4] Lymphocyte count <500 cells/ μ L	Monitor and Stats	Monitor’s list, or, If a patient still receives study treatment after 10 days of latest dose with confirmed lymphocyte count <500 cells/ μ L (defined as a test and a retest within 10 days) If no retest, use the test results
[D5] Platelet count <50,000 cells/ μ L	Monitor and Stats	Monitor’s list, or, If a patient still receives study treatment after 10 days of latest dose with confirmed platelet count <50,000 cells/ μ L (defined as a test and a re-test within 10 days) If no retest, use the test results
[D6] Changes in BP defined as sitting systolic BP at \geq 160 mm Hg plus \geq 20 mm Hg increase from baseline (Week 0, Visit 2) and/or diastolic BP at \geq 100 mm Hg plus \geq 10 mm Hg increase from baseline that do not respond following maximal allowed intervention.	Monitor	Monitor’s list

Important Protocol Violation Category/Subcategory	Source to Identify Protocol Violation	Statistical Programming Guidance for Clinical Study Report
[D7] If the investigator decides that the patient should be withdrawn because of a severe AE, an SAE, or a clinically significant change in a laboratory value, the investigational product is to be discontinued, and appropriate measures are to be taken. Lilly or its designee is to be alerted immediately.	Monitor	Monitor's list
[D8] Patient has a clinically significant systemic hypersensitivity reaction after SC administration of investigational product	Monitor	Monitor's list
[D9] Patient becomes pregnant	Monitor	Monitor's list
[D10] The patient develops a malignancy. (No more than 2 nonmelanoma skin cancers over any 12-month period during the study.)	Monitor	Monitor's list
[D11] Patient develops symptoms suggestive of a lupus-like syndrome or is positive for antibodies against double-stranded DNA	Monitor	Monitor's list
[D12] If the patient for any reason requires treatment with another therapeutic agent that has been demonstrated to be effective for the treatment of PsA.	Monitor	Monitor's list
[D13] Enrollment in any other clinical trial involving an investigational product or enrollment in any other type of medical research judged not to be scientifically or medically compatible with this study	Monitor	Monitor's list
[D14] The patient develops active suicidal ideation with some intent to act with or without a specific plan (yes to question 4 or 5 on the "Suicidal Ideation" portion of the C-SSRS) or develops suicide-related behaviors as recorded on the C-SSRS.	Monitor and Stats	Monitor's list, or, If patient still receives study treatment on the same day or after the date with a yes to question 4 or 5 on the "Suicidal Ideation" portion of the C-SSRS or develops suicide-related behaviors as recorded on the C-SSRS.
[D15] The patient develops any condition or contraindication as addressed in the local labelling for adalimumab that would preclude the patient from continuing in this study protocol.	Monitor	Monitor's list

Important Protocol Violation Category/Subcategory	Source to Identify Protocol Violation	Statistical Programming Guidance for Clinical Study Report
[D16] The investigator decides that the patient should be withdrawn from the study	Monitor	Monitor's list
[D17] The patient requests to be withdrawn from the study	Monitor	Monitor's list
[D18] The investigator or Lilly stops the patient's participation in the study or Lilly stops the study for medical, safety, regulatory, or other reasons consistent with applicable laws, regulations, and GCP.	Monitor	Monitor's list
[D19] The patient becomes HBV DNA positive.	Monitor	Monitor's list
[D20] The patient is diagnosed with an active TB infection.	Monitor	Monitor's list
Category: Study Procedures		
Sub-Category: Excluded Con-meds	Monitor and Stats	Either from monitor's list, or If patient takes prohibited concomitant medication. Note: Prohibited concomitant medication (with details of dose restrictions) will be provided by medical in a separate file.
Sub-Category: Lab/Imaging Criteria		
Missing lab chemistry and hematology: missing baseline or not having at least 1 post-baseline	Monitor and Stats	Monitor's list; or If missing lab chemistry and hematology baseline or not having at least 1 post-baseline
Sub-Category: Other		
Missing ACR or PASI	Monitor and Stats	Monitor's list; or If missing any ACR or PASI data at any visit (Weeks 0 through 52).
Missing C-SSRS any visit except Visit 1	Monitor and Stats	From monitor's list; if missing C-SSRS at any visit except Visit 1
Had unqualified site personnel perform clinical safety and/or efficacy assessments	Monitor	Monitor's list
Unblinding of the blinded rater at the site	Monitor	Monitor's list

Category: Investigational Product		
Sub-Category: Treatment Assignment/Randomization Error		
Took incorrect study medication	Monitor and Stats	Monitor's list; or If IWRS study drug dispense data not match with the treatment label identifier on the Exposure as Collected eCRF page
Sub-Category: Compliance	Monitor and Stats	Monitor's list; or If non-compliant with study medication regimen or over-dose during the treatment period. Note: Non-compliance with therapy is defined to be missing more than 20% of expected doses and missing 2 or more consecutive doses; over-dose is defined as to take more injections at the same time point than specified in the protocol.
Sub-Category: Patient took medication not fit for use	Monitor	Monitor's list
Sub-Category: Other		
Randomized but did not take any study medication	Monitor	Monitor's list
Sub-Category: Treatment Assignment /Randomization Error		
Stratification error leading to incorrect dosing regimen	Monitor and Stats	Monitor's list; or If IWRS stratification data does not match patients' severity of plaque psoriasis (PASI, sPGA and BSA)

Abbreviations: AE = adverse event; ACR = America College of Rheumatology; ALT = alanine aminotransferase; AST = aspartate aminotransferase; ATC = anatomical therapeutic chemical; BCG = Bacille de Calmette et Guérin; bDMARD = biologic disease-modifying antirheumatic drug; bHCG = beta-human chorionic gonadotropin; BP = blood pressure; BSA = body surface area; CASPAR = classification for psoriatic arthritis; CRF = case report form; C-SSRS = Columbia Suicide Severity Rating Scale; csDMARD = conventional synthetic disease-modifying antirheumatic drug; CVA = cerebrovascular accident; DNA = deoxyribonucleic acid; ECG = electrocardiogram; eCRF = electronic case report form; FSH = follicle-stimulating hormone; GCP = good clinical practice; HCV = hepatitis C virus; HIV= human immunodeficiency virus; IL = interleukin; IV = intravenous; IWRS = interactive web-response system; JAK = Janus kinase; MI = myocardial infarction; MTX = methotrexate; NSAID = nonsteroidal anti-inflammatory drug; NYHA = New York Heart Association; PASI = Psoriasis Area and Severity Index; Ps = psoriasis; PsA = psoriatic arthritis; PUVA = psoralen ultraviolet A; SAE = serious adverse event; SC = subcutaneous; SJC = swollen joint count; TB = tuberculosis; TJC = tender joint count; TNF = tumor necrosis factor; ULN = upper limit of normal; UVB = ultraviolet B; WBC = white blood cell; WHO = World Health Organization.

The term “Monitor” indicates the protocol deviation will be identified by site monitors and entered into monitor’s list using a spreadsheet. The spreadsheet will be exported as Study Data Tabulation Model (SDTM) DV domain.

The term “Stats” indicates the protocol violation will be programmed based on data in clinical database by statistical programmers with the statistical programming guidance provided as the last column. The detailed programming specification will be documented in Analysis Data Model (ADaM) specification.

The terms “Monitor and Stats” indicates the protocol deviation will be a combination of monitor’s list (SDTM.DV domain) and statistical programming from clinical database, the deviation will show if either source identifies.

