3.2. Background

PsA is an immune-mediated chronic inflammatory disorder commonly associated with psoriasis (Ps) that occurs in 0.04% to 1% of the general population but in 6% to 42% of patients with psoriasis. It is a progressive, destructive disease that results in deformities, impaired physical function, loss of QoL, and increased mortality (Kavanaugh et al 2016). PsA also has a considerable negative impact on multiple physical and emotional aspects of patients' lives (Gladman et al. 2005; Rosen et al. 2012). Patients with PsA have reported poorer health-related QoL compared to the general population and to Ps patients (Husted et al. 1997; Rosen et al. 2012) and suffer from a similar level of functional impairment to patients with rheumatoid arthritis (RA) (Husted et al. 2013).

The current standard of care for PsA includes nonsteroidal anti-inflammatory drugs; intra-articular and/or systemic glucocorticoids; conventional synthetic disease-modifying

anti-rheumatic drugs (csDMARDs) such as MTX, sulfasalazine (SSZ), leflunomide, and cyclosporine A; and biologic agents such as TNF inhibitors (Gossec et al. 2012; Smolen et al. 2014, Gossec et al. 2016). Although leflunomide has been shown to be effective in improving signs and symptoms of PsA as assessed by Psoriatic Arthritic Response Criteria (PsARC) and American College of Rheumatology 20 score (ACR20), there is only weak evidence that other csDMARDs are effective, though limited controlled clinical trial data are available (Gossec et al. 2012; Mease and Armstrong 2014, Gossec et al. 2016). In a recent randomized controlled trial of patients with PsA treated with MTX, no significant improvement was demonstrated in peripheral arthritis (Kaltwasser et al. 2004, Kingsley et al. 2012). Additionally, csDMARDs have not demonstrated efficacy in treating axial involvement, enthesitis, or dactylitis, though limited data are available (Gossec et al. 2012; Mease and Armstrong 2014). SSZ was effective for axial manifestations in an open-label trial, but not for enthesitis or dactylitis (Clegg et al. 1996; Dougados et al. 1995). Data on radiographic progression on MTX has not been conclusive and only analyzed in a small case-control study; for SSZ, radiographic progression was not prevented in a small case-control study of 20 SSZ-treated patients and 20 matched controls (Ash et al. 2012).

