6.1. Inclusion Criteria

Patients are eligible to be included in the study only if they meet all of the following criteria at screening:

Type of Patient and Disease Characteristics

Patients with a documented diagnosis of PsA for at least 6 months fulfilling the Classification for Psoriatic Arthritis (CASPAR) and the activity of disease as defined by the presence of at least 3 swollen joints (66 joints) and 3 tender joints (68 joints) in patients who are bDMARD naive. Patients must have active psoriatic skin lesions (plaque) of plaque psoriasis with a BSA of at least 3%

Patient Characteristics

- [1] Are male or female patients 18 years or older
 - [1a] Male patients agree to use a reliable method of birth control during the study.
 - [1b] Female patients:

Are women of childbearing potential who test negative for pregnancy and agree to use a reliable method of birth control or remain abstinent during the study and for at least 12 weeks after the last dose of investigational product, whichever is longer. Methods of contraception considered acceptable when used properly include oral contraceptives, contraceptive patch, injectable or implantable contraceptives, intrauterine device, vaginal ring, diaphragm with contraceptive gel, or condom with contraceptive foam.

OR

Are women of nonchildbearing potential, defined as:

Women who have had surgical sterilization (hysterectomy, bilateral oophorectomy, or tubal ligation);

OR

Women who are \geq 60 years of age;

OR

Women ≥40 and <60 years of age who have had a cessation of menses for ≥12 months and a FSH test confirming nonchildbearing potential (≥40 mIU/mL).

- [2] Have a documented diagnosis of PsA for at least 6 months and currently meet the CASPAR classification criteria.
- [3] Have active PsA defined as the presence of at least 3/68 tender and at least 3/66 swollen joints at Visit 1 (Screening) and Visit 2 (Week 0).
- [4] Have active psoriatic skin lesions (plaque psoriasis) with a BSA \geq 3% at Visit 1 (Screening) and Visit 2 (Week 0).
- [50] Have had an inadequate response when treated with 1 or more csDMARDs.

Informed Consent

[5] Have given written informed consent approved by Lilly, or its designee, and Institutional Review Board/Ethical Review Board (ERB) governing the site.

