6.2. Exclusion Criteria

Patients will be excluded from study enrollment if they meet any of the following criteria at screening:

- [6] Are currently enrolled in any other clinical trial involving an investigational product or any other type of medical research judged not to be scientifically or medically compatible with this study
- [7] Have received any prior, or are currently receiving, treatment with any bDMARD therapy or small-molecule for PsA or for psoriasis, including investigational therapies (such as but not limited to TNF inhibitors, IL-1 receptor antagonists, IL-6 inhibitors, anti-IL-12/23p40 therapies, T cell or B cell targeted therapies, or Janus kinase inhibitors).
 - Exception: previous treatment of phosphodiesterase type 4 inhibitors will be permitted. Treatment with phosphodiesterase type 4 inhibitors must have been discontinued at least 8 weeks before randomization (Visit 2).
- [8] Have previously completed or withdrawn from this study or any other study investigating ixekizumab or other IL-17 inhibitors, eg, anti-IL-17 or anti-IL-17 receptor (anti-IL-17R) monoclonal antibodies.
- [9] Have a history of drug-induced Ps.
- [10] Have used csDMARDs other than MTX, leflunomide, sulfasalazine, or cyclosporine in the 8 weeks prior to randomization (Visit 2).
 - Have discontinued MTX, sulfasalazine, or cyclosporine within 12 weeks prior to randomization.

If taking MTX, leflunomide, sulfasalazine, or cyclosporine, must have been treated for at least 12 weeks prior to randomization *and* on a stable dose for at least 8 weeks prior to randomization, as follows: oral or parenteral MTX = 10 to 25 mg/week, leflunomide = 20 mg/day, sulfasalazine = up to 3 g/day, or cyclosporine up to 5 mg/kg/day. The dose of these allowed concomitant medications must remain unchanged during the first 24 weeks of the Open-Label Treatment Period unless changes are required for safety issues. Local standard of care should be followed for concomitant administration of folic acid with MTX.

- [11] Have discontinued leflunomide within 4 weeks prior to randomization or have received leflunomide from 4 to 12 weeks prior to randomization and have not undergone a drug elimination procedure.
- [12] Use of oral corticosteroids at average daily doses of >10 mg/day of prednisone or its equivalent, or use of variable doses of any oral corticosteroids, within 4 weeks prior to randomization (Visit 2).

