[1b] Are women of non-childbearing potential, defined as either women who have had surgical sterilization or who are ≥60 years of age	Monitor	Monitor’s list: women who have had surgical sterilization.
[2] No confirmed diagnosis of PSA of at least 6 months prior to baseline or did not meet CASPAR criteria	Monitor	Monitor’s list
[3] <3 TJC or <3 SJC at Visit 1 or 2	Monitor	Monitor’s list.
[4] BSA <3% at Visit 1 or 2	Monitor and Stats	Monitor’s list. Check if BSA <3% either at Visit 1 or at Visit 2
[50] Have not been treated with 1 or more csDMARDs	Monitor and Stats	Monitor’s list and stats programming. Check past or present use for MTX, sulfasalazine, leflunomide, or hydroxychloroquine

Important Protocol Violation Category/Subcategory	Source to Identify Protocol Violation	Statistical Programming Guidance for Clinical Study Report
[6] Currently enrolled in any other clinical trial involving an investigational product or any other type of medical research judged not to be scientifically or medically compatible with this study	Monitor	Monitor’s list.
[7] Have received prior or currently receiving treatment with any biologic or small molecule therapy for PsA or Ps, including investigation therapies (such as, but not limited to, a TNF inhibitor, IL-1 receptor antagonists, IL-6 inhibitor; anti-IL-12/23p40, T cell or B cell targeted therapies, or Janus kinase inhibitors). Note: previous treatment of phosphodiesterase type 4 inhibitors will be permitted. Treatment with phosphodiesterase type 4 inhibitors must have been discontinued at least 8 weeks before randomization (Visit 2).	Monitor	Monitor’s list
[8] Previous or current medication exposure at Visit 1 to LY2439821 or IL-17 antagonists or previous participation in the current study. (Note: See protocol for patients who may be allowed to re-screen.)	Monitor	Monitor’s list
[9] Have history of drug-induced Ps.	Monitor	Monitor’s list
[10] Use of csDMARDs (other than MTX, leflunomide, sulfasalazine, or cyclosporine) within 8 weeks prior to Visit 2; or have discontinued MTX, leflunomide, sulfasalazine, or cyclosporine within 12 weeks prior to Visit 2.	Monitor	Monitor’s list
[11] Have discontinued leflunomide within 4 weeks prior to Visit 2 or from 4 to 12 weeks prior without drug elimination procedure.	Monitor and Stats	Monitor’s list, or, If the difference between Visit 2 date and medication end date <28 days for previous therapy, Leflunomide

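### The csDMARD eligibility checks in SAP Table RHCF.6.9 ([50] and [10]) do not match the protocol criteria that they are meant to police

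*SAP*

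**What the plan says.** **Criterion [50].** Protocol 6.1 sets the inclusion condition as "Have had an inadequate response when treated with 1 or more csDMARDs". SAP 6.17, Table RHCF.6.9, words the violation as "Have not been treated with 1 or more csDMARDs". Its source is the monitor's list together with statistical programming, and the programming rule reads "Check past or present use for MTX, sulfasalazine, leflunomide, or hydroxychloroquine".

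**Which drugs count.** Protocol 3.2 refers to "anti-rheumatic drugs (csDMARDs) such as MTX, sulfasalazine (SSZ), leflunomide, and cyclosporine A". Protocol 6.2 [10] and Tables RHCF.7.2 and RHCF.7.3 name the same four drugs as the csDMARDs allowed alongside study treatment. Hydroxychloroquine is in none of these lists.

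**Criterion [10].** The protocol's 12-week discontinuation rule is "Have discontinued MTX, sulfasalazine, or cyclosporine within 12 weeks prior to randomization". Leflunomide is left to [11], which excludes patients who stopped it within 4 weeks, or who "have received leflunomide from 4 to 12 weeks prior to randomization and have not undergone a drug elimination procedure". The SAP row for [10] reads "or have discontinued MTX, leflunomide, sulfasalazine, or cyclosporine within 12 weeks prior to Visit 2". The SAP row for [11], directly below, keeps the elimination-procedure exception.

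**Use of the flags.** SAP 6.17 lists important deviations by patient, tabulates them by arm, and plans additional analyses of the primary and/or major secondary endpoints in patients without any, or without some, of the violations.

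**The concern.** A deviation table should restate the protocol's criteria so that they can be checked. Here one row tests a different construct (exposure in place of failure), the same row uses a different drug list, and another row widens a rule that the protocol and the neighbouring SAP row both state more narrowly. Some eligible patients can be reported as important violators, and some ineligible ones can pass unreported.

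SAP 6.1.3 defines no per-protocol population, and SAP 6.7 runs the ACR50 noninferiority test on the ITT population with nonresponder imputation. The additional analyses without violators are therefore the only per-protocol-type check on the noninferiority conclusion, so their membership should follow the protocol.

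**Working it through.** No arithmetic is involved. The check sets the current protocol text beside the SAP rows and classifies four example patients under each.

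Two features of Table RHCF.6.9 matter. Rows marked as monitor only have no program. For rows marked as both monitor and statistics, the table's notes say that a deviation is shown if either source finds it. Row [10] is monitor only; rows [50] and [11] use both sources.

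| Patient | Protocol | SAP label | SAP program |
|---|---|---|---|
| (a) Methotrexate only, adequate response | Fails [50] | [50]: no violation | [50]: not flagged |
| (b) Cyclosporine only, inadequate response | Meets [50] | [50]: no violation | [50]: flagged |
| (c) Hydroxychloroquine only, inadequate response | Not settled: [50] names no drugs, and no current csDMARD list includes it | [50]: depends on the same question | [50]: not flagged |
| (d) Leflunomide stopped 4 to 12 weeks before randomization, with a drug elimination procedure | Not excluded by [10] or [11] | [10]: violation; [11]: no violation | [10]: none exists; [11]: not flagged |

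Reasoning for each:

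- **(a)** The label and the program both ask only whether a csDMARD was ever taken. The patient can still be reported if a monitor applies protocol [50], but nothing in the SAP row asks for that.
- **(b)** Cyclosporine is missing from the [50] program, although SAP [10] in the same table treats it as a csDMARD. Because either source is enough, a correct judgement by the monitor cannot remove the programmed flag.
- **(c)** The program accepts hydroxychloroquine. The amendment that added [50] (Protocol Appendix 5) also took hydroxychloroquine out of exclusion [10] and the concomitant-medication tables, giving as its reason that it was no longer counted as a csDMARD. That reason is recorded against those sections and not against [50].
- **(d)** The only programmed leflunomide rule is in SAP [11]. It looks for an end date less than 28 days (4 × 7) before Visit 2, so it cannot reach a stop at 4 to 12 weeks. The conflict is in the wording of SAP [10] alone.

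**The case against.** The strongest reply is that these rows are shorthand and the protocol governs. Monitors check eligibility against the protocol, inadequate response is a clinical judgement that a program can hardly derive, and an exposure check is a reasonable backstop. Many eligibility rows, such as [2], [3] and [7], have no program at all. The planning rates in Protocol 10.1 come from a csDMARD-experienced population, which is what an exposure check tests. All ITT results stand regardless.

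Much of this is right, and it rules out several stronger readings that a reader might infer:

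- That patients without an inadequate response can never be flagged. Row [50] also uses the monitor's list, so they can be.
- That leflunomide patients are misclassified by program. Row [10] is not programmed; the false flag arises only if monitors follow the SAP wording over the protocol's. Patients on stable leflunomide are not affected at all.
- That hydroxychloroquine must be struck out. Protocol [50] lists no qualifying drugs, the list in Protocol 3.2 is illustrative, and protocol [10] itself speaks of csDMARDs other than the four named. The text supports reconciling the lists, not deciding the question.
- That the sample-size assumptions are undermined. They rest on experience of csDMARDs, not on failure.

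The reply does not remove the false flag for cyclosporine, which is built into the program. It also does not explain why the SAP label drops the inadequate-response condition, or why SAP [10] contradicts SAP [11].

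**Conclusion.** The mismatches are present in the current text and are wrong as written. The cyclosporine omission is the firmest, because its false flag follows from the program with no human step. The replacement of inadequate response by exposure is equally plain in the wording, though a monitor can compensate. The leflunomide conflict is one of wording, in a monitor-only row. The hydroxychloroquine entry is an unresolved inconsistency and not a proven error.

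The reach is narrow: the deviation listing, the summary by arm, and the additional analyses without violators. Even for those analyses the effect depends on which violations are chosen, since SAP 6.17 allows any or a subset and does not name the subset. A reader might infer that the primary or major secondary results are at risk. They are not: SAP 6.12.1 bases them on the ITT population, and no deviation flag enters them. The documents give no counts for any of the four patient types, so no number of misclassified patients can be stated. The conclusion assumes only that the protocol text is the reference for eligibility; it does not judge which eligibility rule is clinically right.

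**What to change.** In SAP Table RHCF.6.9:

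1. Reword [50] as absence of an inadequate response to at least one csDMARD, identified from the monitor's list or the eligibility record. Keep the programmed exposure check as a backstop only.
2. Add cyclosporine to that check. Reconcile hydroxychloroquine with the protocol's csDMARD list and record the decision.
3. Align [10] with protocol [10] by removing leflunomide from the 12-week rule, and leave leflunomide to [11].

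Do not replace the exposure check with the reason for stopping earlier therapy (summarized under SAP 6.9.2) on its own. The protocol permits ongoing stable csDMARDs and stratifies on their use, so a patient may still be taking the drug to which the response was inadequate and would have no stopping reason for it.

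The cost is an edit to two table rows and one line of programming specification. The source for the inadequate-response judgement should be confirmed before the deviation flags are programmed. No change to the design, the ITT analyses or the sample size is needed.
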